9.4 Statistical Analyses

Below is a description of planned statistical analyses. Further details are presented in the Statistical Analysis Plan (SAP).

9.4.1 General Considerations

All statistical analyses will be conducted using SAS, Version 9.4 or later. Baseline characteristics will be summarized by treatment arm. For continuous measures the mean and standard deviation (SD) will be summarized. Categorical variables will be described by the proportion in each category. In addition, 95% confidence intervals (CIs) will be computed as indicated.

All the categorical variables including the primary endpoint will be summarized by treatment with the numbers and percentages of the participants. Treatment difference will be tested using a Cochran–Mantel–Haenszel test stratified by 1) country and 2) participant's clinical status at Baseline. For the categorical endpoints, relative risk and its 95% CI will be presented.

All of the continuous variables, including the changes from Baseline, will be summarized by treatment with the means, SD, medians and the ranges. The mixed model with repeated measurements /analysis of covariance model with treatment, country, participant's clinical status at Baseline and visit as the model term, and Baseline value as the covariate will be used to test for the significance of the treatment difference. Least square means, standard errors, 95% CIs and p-values will be presented.

Time to event endpoints will be analyzed using the Cox Proportional Hazard model with treatment, participant's clinical status at Baseline and country as the model term. The hazard ratio of RESP301+SOC versus SOC will be presented along with 95% CI and p-value from the model. The Kaplan-Meier curves of the time to events will be presented by treatment for each applicable endpoint.

Handling of missing data

If participants are discharged from the hospital prior to Day 14 due to improvement of the clinical status and their status on Day 14 cannot be obtained, their status on Day 14 for the primary endpoint will be imputed with the status on the day of discharge. Depending on the reasons for missing data on the primary endpoint up to Day 14, additional sensitivity analyses will be performed. Further details on handling on missing data will be provided in the SAP.

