6.3 Measures to Minimize Bias: Randomization and Blinding

This is an open-label study; however, the specific intervention to be taken by a participant will be assigned using an interactive voice response system (IVRS)/interactive web response system (IWRS). The site will contact the IVRS/IWRS prior to the start of study intervention administration for each participant. The site will record the intervention assignment on the applicable case report form (CRF), if required.

Potential bias will be reduced using a central stratified randomization to assign participants into one of the study treatment arms, RESP301+SOC or SOC (control), with a randomization ratio of 2:1. Participants will be stratified by country and presence of risk factors for severe outcomes of COVID-19, based on comorbidities and age as follows:

1. Age >65 years
2. Ongoing or currently treated diabetes mellitus
3. Ongoing or currently treated hypertension
4. Ongoing or currently treated cardiovascular disease
5. Ongoing or currently treated chronic lung disease
6. Cancer history of less than 3 years, basal cell skin carcinoma excluded
7. Ongoing or currently treated chronic kidney disease

Participants will be stratified as no risk factor (none of the above criteria), one risk factor (one single of the above) or high-risk factor (2 or more of the above).

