10.5 Appendix 5: Statistical Design Considerations

10.5.1 Some General Design Considerations

1. Binary primary endpoint: progression to critical stage/death up to Day 14
 - to be analyzed by a Cochran-Mantel-Haenszel (CMH) stratified for the factors used in the stratified randomization
 - subjects who withdraw from study treatment will be followed up until their primary endpoint outcome is known (i.e., up to Day 14 or progression to critical stage/death, whatever is first)
 - it is, therefore, not clear what current protocol synopsis text could mean: *If subjects are discharged from the hospital prior to day 14 due to improvement of the clinical status and their status on day 14 cannot be obtained, their status on day 14 for the primary endpoint will be imputed with the status on the day of discharge. and what the implications on statistical study characteristics could be. Further discussion is needed.*

2. Timing of the two planned interim analyses with stopping options is stated as

There are 2 interim analyses planned, the first interim analysis after the first 60 participants have completed day 10 of the observation period ... and a second interim analysis after 150 participants have completed day 14 of the observation period.

With the current text for the timing of the first interim analysis, it is not clear how many subjects will have been randomized at least 14 days prior to the interim data cut-off date and can therefore provide data for the binary primary endpoint (“progression to critical stage/death up to Day 14”).

For such a binary endpoint, Parexel does not recommend including any participant randomized less than 14 days prior to the interim data cut-off date (note this would be different to a study with a time-to-event endpoint) as

- for such participants not yet progressed, the outcome up to Day 14 is unknown and should not be imputed as “not progressed up to Day 14”
- for such participants progressed prior to Day 14, the outcome is known but their inclusion would bias the estimation of progression probability up to Day 14 in an upwards direction.

In order to set up the adaptive group-sequential study design, the following assumptions have been used:

- first interim analysis: a total of ≈ 39 participants randomized at least 14 days prior to data cut-off date
- second interim analysis: a total of $\approx 50\%$ of the initially planned number of participants randomized at least 14 days prior to data cut-off date.

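### The protocol gives two different stratifications for the primary CMH test, and neither includes both the randomization risk group and entry WHO level

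*Protocol*

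**What the plan says.** All of this is in the current protocol, which admits WHO levels 3 and 4.

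- **Randomization (Section 6.3; also the synopsis and Section 4.1).** "Participants will be stratified by country and presence of risk factors for severe outcomes of COVID-19, based on comorbidities and age as follows". The risk factor has three levels: none, one, two or more. Entry WHO level is not a randomization factor.
- **Main analysis text (Section 9.4.1).** Categorical endpoints, expressly including the primary one, get a CMH "test stratified by 1) country and 2) participant's clinical status at Baseline". Continuous endpoints use a mixed model or "analysis of covariance model with treatment, country, participant's clinical status at Baseline and visit as the model term", with the baseline value as covariate. Time-to-event endpoints use a "Cox Proportional Hazard model with treatment, participant's clinical status at Baseline and country as the model term". The risk group is named in none of these.
- **Appendix 5 (Section 10.5.1, item 1).** The primary endpoint is "to be analyzed by a Cochran-Mantel-Haenszel (CMH) stratified for the factors used in the stratified randomization", that is, country and risk group.
- **Design rationale (Section 4.2).** Results are to be stratified by the known risk factors of Section 6.3.
- **Endpoint (Section 9.1).** A move to supplemental oxygen counts as progression only for participants recruited at level 3. Level-4 entrants must reach level 5 or higher.

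**The concern.** Taken at face value, Sections 9.4.1 and 10.5.1 define two primary tests that will in general give different statistics and p-values on the same data. The trial is open-label. Under Appendix 5 the second interim is unblinded, and conditional power decides on futility and sample-size increase. The appendix's own examples fall close to its cut-offs: 50.4% leads to a total of 534 while 50% or less leaves 300, and 3.99% leads to a futility stop. In that setting the test should be fixed unambiguously beforehand.

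Each version also leaves something out. If a factor is used to stratify randomization but not in the test, the arms are balanced on it while the test's variance ignores that balance, so the test is conservative to the degree that the factor is prognostic. If entry level is left out, chance imbalance remains in a variable that now sets the event definition and that randomization does not control.

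**Working it through.** **1. The protocol's own figure.** Inputs from Sections 9.2 and 9.5: 30% v 15%, 2:1 allocation, 80% power, final one-sided alpha 0.0249. The pooled rate is (0.30 + 2×0.15)/3 = 0.20.

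Control n = [1.962×√(1.5×0.20×0.80) + 0.842×√(0.30×0.70 + 0.15×0.85/2)]² / 0.15² = 87.3, so 88, or 264 in total. With continuity correction it is 98, or 294 in total. The stated 300 is reproduced and does not depend on the strata.

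**2. The texts side by side.**

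| Source | Country | Risk group (0/1/2+) | Entry WHO level |
|---|---|---|---|
| Randomization, 6.3 | yes | yes | no |
| CMH, MMRM/ANCOVA, Cox, 9.4.1 | yes | not named | yes, if baseline clinical status means WHO level |
| Primary CMH, 10.5.1 | yes | yes | no |
| Results, 4.2 | – | yes | – |

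The undefined term can be read in two ways:
- *It means WHO level.* The objectives table groups the WHO-scale endpoints under clinical status, which supports this reading. Then 9.4.1 conflicts with 10.5.1 and 4.2 and drops a randomization factor.
- *It means the risk group.* Then 9.4.1 and 10.5.1 agree, but entry level is absent from the primary test.

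A defect remains either way.

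**3. Chance imbalance in entry level.** Assume half the participants enter at level 3; the protocol gives no share. The SD of the between-arm difference is √[0.5×0.5×(1/100 + 1/200)] = √0.00375 = 0.061, about 6 percentage points.

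**4. Size and power of the CMH test.** Simulations used N = 300, 2:1 allocation, one-sided 0.0249, control rate 30%, relative risk 0.5 and half the participants at each level. The prognostic odds ratios, risk-group shares and number of countries are assumptions. Each cell shows size / power.

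| Setting (OR per risk step / OR level 4 v 3) | Level, no risk group | Risk group, no level | Both | Power, both minus level |
|---|---|---|---|---|
| No country factor, 2 / 2 | 0.0229 / 86.4% | 0.0255 / 86.7% | 0.0257 / 86.9% | +0.5 |
| No country factor, 3 / 3 | 0.0196 / 87.4% | 0.0259 / 87.9% | 0.0263 / 88.7% | +1.3 |
| Three countries, 1.5 / 1.6 | 0.0230 / 86.0% | 0.0232 / 86.2% | 0.0247 / 85.8% | −0.3 |
| Three countries, 2.2 / 2.7 | 0.0235 / 87.1% | 0.0267 / 87.0% | 0.0280 / 87.1% | +0.1 |
| Three countries, 3.3 / 4.5 | 0.0198 / 87.3% | 0.0263 / 87.1% | 0.0277 / 88.5% | +1.3 |

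Risk shares are 25/35/40% in the first two rows and 25/30/45% in the others. Countries are split 60/30/10%, and the odds ratios in the last three rows are exponentials of the log-odds used (0.4/0.5, 0.8/1.0, 1.2/1.5). A further three-country run, level against both, gave 85.6% v 85.1% at odds ratios of 1.5, 85.8% v 85.8% at 2, and 86.8% v 87.6% at 3: differences of −0.5, 0.0 and +0.8.

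Monte Carlo error: the first two rows used 200,000 trials for size, SE √(0.0249×0.9751/200,000) = 0.00035, so 0.0263 is a real, small excess of 0.0014. The last three rows used 6,000 trials, SE 0.0020, so their sizes are only rough.

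**5. Sparseness.** The number of countries is not stated. With three, all factors together make 3×3×2 = 18 strata: 300/18 ≈ 17 participants each at the end and 150/18 ≈ 8 at the second interim.

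**The case against.** The strongest reply is that 9.4.1 may not omit the risk group at all. The same sentence stood in the earlier protocol version included in the same file, when every entrant was at level 4. WHO level was then a constant and could not be a stratum. The two-item list also parallels the two randomization factors. On that reading 9.4.1, 4.2 and 10.5.1 agree. This stands as a real ambiguity, so a reader should not infer that the primary test certainly ignores the risk group. It does not clear the text: the term is undefined, and on that reading nothing adjusts the primary test for entry level.

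Second, Appendix 5 is partly advisory. It says further discussion is needed, and its item 1 still describes the pre-amendment endpoint. Section 9.4 defers detail to the SAP, which may already name one test. That limits any claim that the choice is open once data are seen. But the protocol does state strata, Sections 9.2 and 9.5 send the reader to Appendix 5, and an SAP following the protocol would have to depart from one of the two passages.

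Third, a reader might infer a meaningful loss of power or a threat to type I error. The calculations do not support that. Leaving out the risk group never pushed size above nominal, the power difference vanishes or reverses under weaker prognostic effects, and every option stays above 80%. That either factor is strongly prognostic is an assumption; the protocol gives no such figure. The fully stratified test is the one whose size can run slightly high.

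Finally, for change on the WHO scale the mixed model already carries the baseline value, so entry level is adjusted for there on any reading.

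**Conclusion.** The point holds as an inconsistency to be corrected. The protocol words the strata of its primary test in two incompatible ways unless an undefined term is read against its natural meaning. On either reading one of two relevant factors is missing: the randomization risk group, or the entry level that determines the event definition.

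The size is modest. With assumed odds ratios of 2–3 per step, omitting the risk group gives a one-sided size of about 0.019–0.023 against 0.0249. Using all three factors instead of country and level changes power by about −0.5 to +1.3 points, depending on assumed prognostic strength and number of countries, and its size ran at about 0.024–0.028. The planned 300 is unaffected. The argument is for one clearly stated test that respects the randomization, not for a material gain in power.

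**What to change.** State one stratification, in identical words, in Sections 9.4.1 and 10.5.1: country, randomization risk group (0, 1, 2+) and entry WHO level (3 v 4). Replace the baseline clinical status term with entry WHO level wherever it appears. Use the same terms in the MMRM/ANCOVA and Cox models; for change on the WHO scale, entry level and the baseline value are the same variable, so one term is enough. Pooling of small countries can be left to the SAP.

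The cost is wording only. Both variables are already collected, and neither the sample size nor the randomization system has to change. The price is sparser strata, especially at the second interim, and a size that can run slightly above nominal, so the SAP's pooling rule should be set before that interim.

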Study intervention, TID ⁶		X	X	X				A staggered dosing approach will be used for the first 10 participants (up to the first IDMC safety review). Each RESP301 dose will be administered by intermittent inhalation to monitor the tolerability and response to RESP301 (see Sections 6.1 and 9.6). Where possible study intervention should be administered at approximately the same times each day At least 6 hours between 2 consecutive doses
AE/SAE review	X	X	X	X	X	X	X	
Concomitant medication review	X	X	X	X	X	X	X	
Pre Treatment oxygen / respiratory assessment ⁷	X	X	X	X				
SpO ₂ on room air (after at least 1 minute) prior to study intervention administration and immediately at the end of nebulization ⁶		X	X	X				See Section 8.1.2

Procedure	Screening (up to 48 hours before Day 1 ¹)	Intervention Period			Early withdrawal	Efficacy follow-up (Day 14) ² (± 2 days)	EoS efficacy and safety follow-up (Day 28) ² (± 2 days)	Notes
		Day 1 ¹	Daily while hospitalized	Day 10 / hospital discharge				
Modified WHO ordinal scale	X	X	X	X		X	X	See Section 8.1.1
NEWS 2 assessment ⁷		X	X	X				Prior to study intervention in the morning. See Section 8.1.3

Abbreviations: AE=adverse event; aPTT= activated partial thromboplastin time; CBC=complete blood count; Chem 7=blood chemistry panel (sodium, potassium, chloride, bicarbonate/CO₂, blood urea nitrogen, creatinine, glucose); CV=cardiovascular; ECG=electrocardiogram; IDMC=Independent Data Monitoring Committee; LFTs=liver function tests; mHb=methemoglobin; PT/INR=prothrombin time/international normalized ratio; RT-PCR=reverse transcription-polymerase chain reaction; SAE=serious adverse event; TID=three times daily.

1. Screening and randomization may be on the same day, providing all eligibility criteria are met.
2. For participants who are already discharged at either the Day 14 or Day 28 (EoS) follow-up, there will be a phone call to check AEs/SAEs, concomitant medications, and modified WHO ordinal scale. At EoS, safety laboratory tests (nitrite and mHb only) and weight will be collected for participants in hospital only.
3. COVID-19 infection must be confirmed and documented in chart with a positive result on a validated test.
4. At Screening: CBC, chem 7, mHb, LFTs, and coagulation (PT/INR, aPTT).
On Day 1, Day 3, Day 7 and Day 10, or early withdrawal: CBC, chem 7 (per SOC), and mHb.
On Day 28: nitrite and mHb (participants in hospital at EoS only).

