8.1 Efficacy Assessments

8.1.1 Modified WHO Ordinal Scale

A modified WHO ordinal scale will be used for consistency with the recent study of lopinavir-ritonavir in adults hospitalized with severe COVID-19 (Cao et al, 2020), to record the participant's status at the time of assessment. The modified WHO ordinal scale includes the following levels:

1. Not hospitalized, no limitations on activities;
2. Not hospitalized, limitation on activities;
3. Hospitalized, not requiring supplemental oxygen;

4. Hospitalized, requiring supplemental oxygen;
5. Hospitalized, on non-invasive ventilation or high-flow oxygen devices;
6. Hospitalized, on invasive mechanical ventilation or extra corporeal membrane oxygenation (ECMO);
7. Death.

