9.1 Statistical Hypothesis

RESP301 reduces the rate of progression in the modified WHO ordinal scale in COVID-19 (see Section 8.1.1).

The endpoint of worsening level on the WHO ordinal scale represents a composite endpoint of scales above the entry level, being (i) death (level 7), (ii) hospitalized, on invasive mechanical ventilation or ECMO (level 6), (iii) hospitalized, on non-invasive ventilation or high-flow oxygen devices (level 5) , or, for those patients who were recruited at WHO ordinal scale 3, (iv) hospitalized, requiring supplemental oxygen.

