9.4.2 Primary Endpoint

The primary endpoint is the proportion of participants who progress by at least one level higher on the modified WHO ordinal scale by Day 14.

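### Section 10.5.1 and the discharge rule in 9.4.1 conflict with the primary endpoint of worsening by at least one WHO level by Day 14, and some counted events are not captured

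*Protocol*

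**What the plan says.** The current version, which admits level 3 and level 4 participants, states the endpoint consistently in Sections 1.1, 3, 9.2, 9.4.2 and 10.5.3: a participant is an event if they "progress by at least one level higher on the modified WHO ordinal scale by Day 14". Section 9.1 spells out the composite as levels 5 to 7 for everyone and, "for those patients who were recruited at WHO ordinal scale 3, (iv) hospitalized, requiring supplemental oxygen".

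Two places depart from this.

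- Section 10.5.1, item 1, opens with "Binary primary endpoint: progression to critical stage/death up to Day 14". The same item then reproduces the discharge-imputation sentence, says its meaning and its statistical implications are unclear, and closes with "Further discussion is needed".
- Section 9.4.1, under the handling of missing data, covers participants discharged with improvement before Day 14 whose Day 14 status cannot be obtained: "their status on Day 14 for the primary endpoint will be imputed with the status on the day of discharge".

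On data capture, Section 8.1.1 has the scale record the participant's "status at the time of assessment". The row "Modified WHO ordinal scale" in the Section 1.3 schedule is marked at screening, on Day 1, daily while hospitalized in the intervention period, at Day 10 or discharge, and then at the Day 14 and Day 28 contacts.

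**The concern.** The primary endpoint is binary, so the protocol must settle for each participant whether an event occurred. Here the answer can depend on which section the programmer follows. A level-3 entrant who starts low-flow oxygen is an event under 9.1 and 9.4.2 but, on the ordinary meaning of the words, not under 10.5.1. A participant who reached level 5 on Day 4, recovered, went home on Day 9 and could not be reached is an event under 9.4.2, yet becomes a non-event if 9.4.1 is applied as written.

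The discharge rule works in one direction only: within the group it covers, it always yields no progression. The trial is open-label, so a difference between arms in discharge timing or reachability would turn lost events into bias as well as lost power. Finally, 9.4.2 counts worsening at any point up to Day 14, but part of that interval is seen only through a single status reading.

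**Working it through.** **Passages side by side** (entry level 3 or 4; discharged means level 1 or 2, Section 8.1.1)

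| Course of the participant | 9.1 and 9.4.2 | 10.5.1 item 1 | 9.4.1 read literally |
|---|---|---|---|
| Level 3 to 4, stays in hospital to Day 14 | event | not an event | rule does not apply |
| Level 3 to 4, recovers, discharged before Day 14, unreachable | event | not an event | not an event |
| Level 4 to 5, recovers, discharged before Day 14, unreachable | event | event, if level 5 counts as critical | not an event |
| Never worsens, discharged before Day 14, unreachable | unknown after discharge | unknown after discharge | not an event |

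Only the last row is a true missing-data case. In the second and third rows the outcome was settled before discharge. Section 10.5.1 supports that logic, since it follows participants "up to Day 14 or progression to critical stage/death, whatever is first".

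**Capture.** After Day 10 (or after discharge, if earlier) the next scheduled score is the Day 14 contact, which records status at that moment. A worsening that starts and resolves in between has no scheduled record.

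**The plan's own power figure.** Inputs from Section 9.2: 30% v 15%, 100 v 200 participants, one-sided alpha 0.025, about 80% power. With the pooled-variance formula, power = Φ((p1 − p2 − 1.96·SE0)/SE1):

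- SE0 = √(0.20 × 0.80 × (1/100 + 1/200)) = 0.0490
- SE1 = √(0.30 × 0.70/100 + 0.15 × 0.85/200) = 0.0523
- power = Φ((0.15 − 0.0960)/0.0523) = Φ(1.03) = 84.9%

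With a continuity correction, power is 81.3% and N is 291. The stated figure reproduces, so the fault is not in the sample-size arithmetic.

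**Effect of losing events.** At the planned rates 30 events are expected per arm, 60 in all. Suppose a share e of events stops counting, equally in both arms. The documents do not give e; the values are assumptions.

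| e | Rates compared | Power (pooled) |
|---|---|---|
| 0 | 30% v 15% | 84.9% |
| 2% | 29.4% v 14.7% | 84.0% |
| 5% | 28.5% v 14.25% | 82.6% |
| 10% | 27% v 13.5% | 80.1% |

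**A borderline example.** Two-proportion z test, 100 control v 200 active, judged against the final nominal alpha of 0.0249 (Section 9.5). The counts are chosen to lie near the boundary.

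| Events, control v active | One-sided p, unpooled | One-sided p, pooled |
|---|---|---|
| 30 v 40 | 0.0317 | 0.0268 |
| 30 v 39 | 0.0253 | 0.0208 |
| 30 v 38 | 0.0200 | 0.0160 |
| 29 v 38 | 0.0300 | 0.02497 |

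Reclassifying two active-arm progressors (unpooled) or one (pooled) moves 30 v 40 across the boundary. If one control event is also lost along with two active ones (29 v 38), neither test succeeds. At the planned counts of 30 v 30 the unpooled p is 0.002, and losing two active events changes no conclusion.

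**The case against.** The strongest reply is that the endpoint is stated the same way in five sections and its composite is spelled out in a sixth. The 10.5.1 wording looks like a leftover from the level-4-only version. The 9.4.1 sentence is a missing-data rule for a narrow group, not a definition, and a participant with a recorded worsening has no missing outcome. Reaching the affected group takes progression, recovery, discharge before Day 14 and failure of the contact attempts in Section 7.4. Other missing data are left to sensitivity analyses and the SAP.

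Most of this stands, and it rules out several stronger readings:

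- **Three rival definitions.** There is one main definition, one stale definition, and one imputation rule with a missing condition.
- **Planning rates without an endpoint.** A reader might infer this because Appendix 5 lists 30% and 15% a few items after the stale wording. Section 9.2 ties them to progression by at least one level.
- **Interim conditional power on the old endpoint.** Section 10.5.3 names the current endpoint for that calculation.
- **All missing data resolved as success.** The rule covers only participants discharged with improvement.
- **The p-value example as the size of the defect.** It uses counts near the boundary, removes events mainly from one arm, and uses an unstratified z test where the plan specifies a stratified Cochran–Mantel–Haenszel test.

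What does not stand is that nothing needs correcting. The 10.5.1 text is current, its comment is still open, and 9.4.1 does not contain the condition that the charitable reading supplies. Deferring detail to the SAP does not reconcile passages already fixed in the protocol.

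**Conclusion.** The point holds in limited form. Section 10.5.1 contradicts the primary endpoint for level-3 entrants and leaves an acknowledged question about it open. The discharge rule in 9.4.1, read literally, can erase a recorded progression. The schedule does not capture worsening after Day 10 or after discharge that resolves by the Day 14 contact.

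The direct effect of the discharge rule is probably small: under the assumed equal losses of 2% to 10%, power falls by about 1 to 5 percentage points. Much larger losses would require Day 14 status to replace cumulative progression for every participant, which the protocol does not say. A difference in losses between arms would add bias, but no passage shows that one is expected. The p-value example shows only that a borderline result could flip. Correction is still warranted before analysis, because these passages decide who counts as a primary event and the correction costs almost nothing.

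**What to change.** 1. In 9.4.1, 9.4.2 and 10.5.1, state one definition: a participant is a progressor if any assessment after randomization through Day 14 is at least one level above entry level, death included, whatever the later status.
2. In 9.4.1, apply the discharge-status rule only to participants with no recorded progression and no Day 14 contact. Add a sensitivity analysis that counts them as progressors.
3. In 10.5.1, item 1, replace the critical-stage wording with this definition, in the follow-up bullet and the interim-timing text as well, and delete the open comment.
4. At the existing Day 14 call or chart review, record the worst level since the last assessment and its date.

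The cost is protocol wording, one extra sensitivity analysis, and two data fields at a contact that already takes place. No visit, treatment or sample size changes.
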